# 12.2.13. Subgroup Analyses

Subgroup analyses of OS will be performed for potential prognostic and predictive subgroup variables (for example, patients with or without prior immunotherapy).

# 12.2.14. Interim Analyses

### 12.2.14.1. Safety Interim Analyses

The DMC is responsible for providing external oversight of patient safety in Study JPBK independently of the Lilly study team and Lilly GPS.

During the study, safety interim analyses will be performed approximately every 6 months. The safety interim analyses will be conducted to evaluate the overall safety profile of abemaciclib. At the recommendation of the DMC, the frequency of safety interim analyses may be modified.

At each interim analysis, the DMC may recommend the trial continue without modifications, continue with specific modifications, or be stopped for safety concerns. There will be no prespecified rules for stopping the trial due to safety concerns. The DMC members will review unblinded safety data at each interim analysis. If a significant safety signal is identified, the DMC may recommend a protocol amendment, termination of enrollment, and/or termination of study treatment. The recommendations of the DMC will be communicated to the Lilly Senior Management Designee and, if necessary, an Internal Review Committee.

In the event that safety monitoring uncovers an issue that needs to be addressed by unblinding at the treatment group level, members of the DMC can conduct additional analyses of the safety data. Additionally, unblinding of a limited number of Lilly representatives external to the study team may be required for evaluation of selected SAEs for determination of regulatory reporting.

### 12.2.14.2. Efficacy Interim Analyses

One interim efficacy analysis is planned based on the PFS endpoint. This interim analysis is for futility only and will be conducted by the DMC. There is no plan for interim efficacy analysis based on the OS endpoint. The DMC may call for additional, unplanned, interim efficacy analyses. Details of the DMC communication plan can be found in the DMC charter.

The interim efficacy analysis will be conducted after approximately 100 PFS events have occurred. This analysis will be based on the PFS endpoint and will be for futility only. The DMC will be instructed to recommend the study be stopped for futility if the observed hazard ratio for PFS (as calculated using a stratified Cox proportional hazards model) is greater than 0.95.

Only the DMC is authorized to evaluate unblinded interim efficacy and safety analyses. Study sites will receive information about interim results ONLY if they need to know for the safety of their patients.

# 13. Informed Consent, Ethical Review, and Regulatory Considerations

## **13.1. Informed Consent**

The investigator is responsible for ensuring that the patient understands the potential risks and benefits of participating in the study, including answering any questions the patient may have throughout the study and sharing in a timely manner any new information that may be relevant to the patient's willingness to continue his or her participation in the trial.

There may be 2 ICF used in this study: pre-screening ICF and study ICF.

The pre-screening ICF will provide relevant information and documents that the patient is satisfied with his or her understanding of the genetic testing of the tumor sample for *KRAS* mutation status. No procedures will be conducted or treatment provided to patients after signing this pre-screening ICF. Pre-screening is optional; the determination may also be made during screening under the study ICF.

The study ICF will be used to explain the potential risks and benefits of study participation to the patient in simple terms before the patient is entered into the study, and to document that the patient is satisfied with his or her understanding of the risks and benefits of participating in the study and desires to participate in the study. If determination of *KRAS* mutation status by the Study JPBK central laboratory was not completed during a pre-screening period, then the determination will be made during screening under the study ICF. Prior to submitting a request for approval for study entry using a local *KRAS* test result, the study ICF must be signed.

The investigator is responsible for ensuring that informed consent is given by each patient or legal representative. This includes obtaining the appropriate signatures and dates on the ICF prior to the performance of any protocol procedures and prior to the administration of study drug.

As used in this protocol, the term "informed consent" includes all consent and assent given by patients or their legal representatives.

## 13.2. Ethical Review

Lilly or its representatives must approve all ICFs before they are used at the investigative sites. All ICFs must be compliant with the International Conference on Harmonisation (ICH) guideline on GCP.

Documentation of ERB approval of the protocol and the ICF must be provided to Lilly before the study may begin at the investigative sites.

The study site's ERBs should be provided with the following:

- the current IB or package labeling (for example, PI or SmPC) and updates during the course of the study
- ICF
- relevant curricula vitae

## 13.3. Regulatory Considerations

This study will be conducted in accordance with:

- consensus ethics principles derived from international ethics guidelines, including the Declaration of Helsinki and Council for International Organizations of Medical Sciences International Ethical Guidelines
- the ICH GCP Guideline (E6)
- applicable laws and regulations.

The investigator or designee will promptly submit the protocol to applicable ERB(s).

Some of the obligations of Lilly will be assigned to a third-party organization.

An identification code assigned to each patient will be used in lieu of the patient's name to protect the patient's identity when reporting AEs and/or other trial-related data.

## 13.3.1. Investigator Information

Physicians with a specialty in oncology will participate as investigators in this clinical trial.

## 13.3.2. Protocol Signatures

The sponsor's responsible medical officer will approve the protocol, confirming that, to the best of his or her knowledge, the protocol accurately describes the planned design and conduct of the study.

After reading the protocol, each principal investigator will sign the protocol signature page and send a copy of the signed page to a Lilly representative.

## 13.3.3. Final Report Signature

The clinical study report (CSR) coordinating investigator will sign the final CSR for this study, indicating agreement that, to the best of his or her knowledge, the report accurately describes the conduct and results of the study.

Lilly will select an investigator to serve as the CSR coordinating investigator.

The Lilly responsible medical officer and statistician will sign/approve the final CSR for this study, confirming that, to the best of his or her knowledge, the report accurately describes the conduct and results of the study.

# Attachment 1. Protocol JPBK Study Schedule

## Study Schedule, Protocol I3Y-MC-JPBK

Perform procedure as indicated.

			Pre- Screen a	Base	eline	Pat	ients o	n Stud	ly Trea	atment	Postdiscor Follow	
		Cycle	Pre- screening BL	В	L		1		2	3 – n	Short- Term Follow- Up b	Long- Term Follow -Up
		Visit	PRE0	(	)		1	1	2	3 – n	801	802 - 8XX
		Duration (days)		≤,	28	2	28	2	28	28	30	60
		Relative day within a cycle		≤28	≤14	1	15	1	15	1		
Procedure Category	Procedure	Protocol Reference										
Study Entry /Enrollment	Informed Consent Form signed (prior to performance of any protocol-specific tests/procedures)	Section 13.1	Х	Х	ab							
/Em onment	Inclusion/Exclusion evaluation	Section 7	Х		Х							
	Brain scan c	Section 7.1		2	K							
	Initial history/ preexisting conditions				х							
Medical History z	Historical illnesses				Х							
·	Smoking/alcohol habits assessment				Х							
	Height				Х							
	Weight				Х			Х		Х	Х	
Physical Examination z	Blood pressure/pulse	Section 10.3.1			х			х		Х	Х	
	ECOG performance status	Attachment 4			Х	Х		х		Х	Х	
	Tumor measurement (palpable or visible) d	Section 10.1			х			х		х		Xe
Tumor Assessment	Radiologic imaging according to RECIST f	Section 10.1 Attachment 5		2	K					х		Xe
Survival inform	nation	Section 10.1									Х	Xg
Adverse Event Grading h	Collection/CTCAE	Section 10.3			Х	3	x	3	x	х	х	Х

			Pre- Screen a	Base	eline	Pat	tients o	n Study	Treati	ment	Postdiscor Follow	
		Cycle	Pre- screening BL	В	L	1	1	2	2	3 – n	Short- Term Follow- Up b	Long Term Follow -Up
		Visit	PRE0	(	)	1	1	2	2	3 – n	801	802 - 8XX
		Duration (days)		≤2	28	2	8	2	8	28	30	60
		Relative day within a cycle		≤28	≤14	1	15	1	15	1		
Procedure Category	Procedure	Protocol Reference										
Concomitant N	Medication Notation	Section 9.6		2	K	2	X	2	K	Х	Х	
	Central hematology i	Attachment 2			Х	Х	Х	Х	Х	Х	Х	
	Central chemistry i	Attachment 2			Х	Х	Х	Х	Х	Х	Х	
	Local serum pregnancy testj,k	Attachment 2			Х			$\mathbf{x}^{\mathbf{k}}$		$\mathbf{x}^{\mathbf{k}}$		
Lab/	Central pharmacokinetic sampling 	Attachment 7				Х		х		х		
Diagnostic Tests	Pharmacogenetic whole blood sample	Section 10.4.3.2				x aa						
	Plasma sample for circulating biomarkers	Section 10.4.3.3		$\mathbf{x}^{\mathbf{m}}$		x m		x m				
	Local ECG n	Section 10.3.2.1			x°	x p		xq		$\mathbf{x}^{\mathbf{r}}$	x s	
	Archived tumor samples	Section 10.4.2 and 10.4.3.1	$\mathbf{x}^{t}$	x u		x v						
Health	MDASI-LC W	Section 10.2			Х			Х		Х	Х	
Outcomes Assessments	EQ-5D 5L w	Section 10.2			Х			Х		Х	Х	
Study Dwy-	Abemaciclib x	Section 9.1				2	X	У	K	Х		
Study Drug	Erlotinib Y	Section 9.1				2	X	У	K	Х		

Abbreviations: BL = baseline; C1D1 = Cycle 1 Day 1; CNS = central nervous system; CTCAE = Common Terminology Criteria for Adverse Events; ECG = electrocardiogram; ECOG = Eastern Cooperative Oncology Group; EQ-5D 5L = European Quality of Life – 5 Dimensions – 5 Level; FFPE = formalin-fixed paraffin-embedded; ICF = informed consent form; MDASI-LC = MD Anderson Symptom Inventory; MRI = magnetic resonance imaging; OS = overall survival; PK = pharmacokinetics; Q12H = every 12 hours; RECIST = Response Evaluation Criteria in Solid Tumors; SAEs = serious adverse events; V = Visit.

- a The pre-screening period begins when the pre-screening ICF is signed for evaluation of FFPE tissue by Study JPBK central laboratory and ends once the *KRAS* mutation status of the tissue is determined. This period is optional; *KRAS* mutation status can also be determined during screening under the study ICF.
- b Short-term follow up begins the day after the patient and the investigator agree that the patient will no longer continue study treatment and lasts approximately 30 days (± 7 days).
- Patients with a history of CNS metastases must have a brain scan (for example, MRI) within 28 days of randomization to document stability of their CNS metastases, even if there have been no changes in symptoms. If a prior brain scan was completed within 45 days of starting C1D1, the brain scan does not need to be repeated at baseline.

#### Study Schedule, Protocol I3Y-MC-JPBK (continued)

- d Palpable or visual tumor measurement to be performed within 72 hours of start of each cycle if assessed as target/non-target lesions. For visible lesions, a digital photograph is required with a ruler. If the skin lesion is a target lesion, reassessment is performed at each cycle. If the skin lesion is non-target, repeat photographs should be done at every other cycle. Photographs must be performed to document any changes to skin lesions and are sent to central vendor for review.
- e For patients who discontinue study treatment without objectively measured progressive disease, continue to evaluate tumor response approximately every 8 weeks by the same method used at baseline and throughout the study until the patient has objective disease progression, or until the study's final analysis of OS. After the patient has objective disease progression, radiologic tests are no longer required and the patient will be followed up approximately every 60 days (±14 days) until the patient's death or overall study completion.
- f Imaging studies are performed locally and transmitted for central review. Radiological assessment of the chest and abdominal region is performed at baseline (within 28 days of treatment start), then on Day 1 ±7 days of the scheduled Day 1) of every other cycle beginning with Cycle 3 until progressive disease or the start of the next line of anti-tumor treatment. A scan performed up to 30 days prior to the first dose of treatment is permitted as the baseline scan, therefore omitting the baseline scan. If a cycle is delayed, tumor assessment should be concurrent with Day 1 of the new cycle. If the assessment was completed before Day 1 of the next cycle and the patient has a delay in starting the next cycle, the radiological scan does not need to be repeated again when Day 1 of the next cycle is resumed.
- g Collection of survival data and subsequent antitumor therapies. Every 60 days (±14 days). Whenever possible, survival follow-up is conducted in person. If an in-person visit is not possible, the site may confirm survival by contacting the patient directly via phone.
- h Data on SAEs that occur before the end of trial will be stored in the collection database and the Lilly Safety System. During long-term follow-up, only SAEs that are related to protocol procedures or study drug will be collected. All drug- or procedure-related adverse events and serious adverse events should be followed until they resolve, are no longer considered to be drug- or procedure-related, become stable or return to baseline, the patient starts a new therapy, the patient dies, or the patient becomes lost to follow-up. Frequency of evaluation is left to the judgment of the investigator.
- Laboratory assessments should occur on Day 1 (±3 days) of each cycle and Day 15 (± 3 days) of Cycles 1 and 2. If the baseline laboratory assessment was conducted ≤3 days prior to Cycle 1 Day 1, reassessment is not required at Cycle 1 Day 1. For central versus local labs, refer to Attachment 2.
- j Perform pregnancy tests for woman of child-bearing potential.
- k Perform pregnancy tests once every 28 days (±7 days) prior to administration of study drug, where required by local regulations.
-  Sparse PK samples will be collected on Cycle 1 Day 1, Cycle 2 Day 1 and Cycle 3 Day 1 (only for patients receiving abemaciclib).
- m A plasma sample should be collected at baseline at the time FFPE tissue is requested for testing at the Study JPBK central laboratory. Patients who enter the study with a local KRAS test result may omit this baseline sample. Patients that have submitted FFPE tissue during pre-screening may have this baseline sample collected at the time of other blood laboratory samples. Additional samples are collected on all randomized patients at Cycle 1 Day 1 and Cycle 2 Day 1.
- n Local ECG (no replicates required).
- A baseline ECG will be collected from all patients.
- P ECG will be collected from patients receiving abemaciclib only. Two ECG will be collected on Cycle 1 Day 1. The first ECG will be collected predose; the second will be collected 4 to 6 hours postdose. If the patient had a baseline ECG performed within 24 hours of the predose ECG at Cycle 1 Day 1, the scheduled predose ECG may be omitted.
- 9 ECG will be collected from patients receiving abemaciclib only. An ECG will be collected 4 to 6 hours postdose on Cycle 2 Day 1.
- r If the patient received abemaciclib for 6 months, an additional ECG will be collected 4 to 6 hours postdose Cycle 7 Day 1.

#### Study Schedule, Protocol I3Y-MC-JPBK (concluded)

- s ECG will be collected from patients receiving abemaciclib only.
- t Formalin-fixed paraffin-embedded tumor tissue requested after patient signs pre-screening ICF. Eight slides are mandatory for *KRAS* testing by the Study JPBK central laboratory prior to enrollment. If testing did not occur during pre-screening, sample collection and testing is required during baseline visit.
- u If the patient was not pre-screened, FFPE tumor tissue is requested after patient signs the study ICF. Eight slides are mandatory for *KRAS* testing by the Study JPBK central laboratory prior to enrollment. If enrollment using a local *KRAS* result is approved, no further tissue should be submitted to the Study JPBK central laboratory for analysis. Approval for local *KRAS* result is required from the sponsor prior to randomization. Local *KRAS* testing is not a required study procedure.
- v An additional 20 slides or FFPE tumor tissue block requested for biomarker research. If enrollment using a local *KRAS* result is approved, no further tissue should be submitted to the Study JPBK central laboratory for analysis.
- W MDASI-LC and EQ-5D 5L should be administered at baseline (within 14 days of treatment start), on Day 1 of every cycle beginning with Cycle 2, and at the 30-day follow up visit (V801). The preferred order of collection is MDASI-LC and then EQ-5D 5L. Patients should complete before interaction with site staff.
- x Abemaciclib is to be administered every 12 hours (± approximately 2 hours) on Days 1 through 28 of each cycle. On Cycle 1 Day 1 only, patients should take 1 single dose of abemaciclib at clinic and initiate subsequent Q12H dosing from Cycle 1 Day 2 moving forward.
- y Erlotinib is to be administered every 24 hours (± approximately 2 hours) on Days 1 through 28 of each cycle.
- z The medical history and physical examination will be performed by a qualified healthcare provider with assessments that include general appearance, skin, head and neck, respiratory, cardiovascular, abdomen, lymph nodes, thyroid, and musculoskeletal and neurological systems.
- aa Pharmacogenetic whole blood sample should be collected. This may be collected either predose or postdose.
- ab The study ICF must be signed at baseline before any study screening procedures are performed, but this does not have to be within 28 days of treatment start (Cycle 1 Day 1). No window is defined; however, the patient will have to re-sign the study ICF in case it has been updated/revised. The study ICF needs to be signed prior to requesting approval by the sponsor for study entry for those with a local KRAS result.

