#### Figure JPBK.8.1. Illustration of study design.

Terms used to describe the periods during the study are defined below:

- **Pre-screening:** begins when the pre-screening informed consent form (ICF) is signed for evaluation of FFPE tissue by Study JPBK central laboratory and ends once the *KRAS* mutation status of the tissue is determined (or at discontinuation, if the study ICF is not signed). Pre-screening for *KRAS* mutation status determination is optional. If pre-screening did not occur, determination of *KRAS* mutation status will occur at baseline.
- **Baseline:** begins when the study ICF is signed and ends at the first study treatment (or at discontinuation, if no treatment is given).
- **Study Period:** begins at the first study treatment and ends at study completion. The study period does not include the extension period.
  - **Study Treatment Period:** begins at the first study treatment and ends when the patient and the investigator agree that the patient will no longer continue study treatment. The date of this agreement is to be reported on the case report form (CRF) as the Date of Discontinuation from study treatment.
  - **Postdiscontinuation Follow-Up:** begins the day after the patient and the investigator agree that the patient will no longer continue study treatment. All

randomized patients must be followed during postdiscontinuation regardless of whether study treatment was received.

*Short-term follow-up* begins the day after the patient and the investigator agree that the patient will no longer continue study treatment and lasts approximately 30 days.

*Long-term follow-up* begins the day after short-term follow-up is completed and continues until the patient's death or overall study completion. During long-term follow-up, patients will have a follow-up visit every 60 days ( $\pm 14$  days).

- **Extension Period:** begins after study completion and ends at the end of trial. During the extension period, patients on study therapy who continue to experience clinical benefit may continue to receive study therapy until one of the criteria for discontinuation is met. The extension period includes extension period follow-up.
  - Extension period follow-up: begins 1 day after the patient and the investigator agree that the patient will no longer continue treatment in the extension period and lasts approximately 30 days.

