# 9.5. Blinding

This is a randomized, open-label study. Randomization will occur using an interactive web response system. Assignment to treatment groups will be determined by a computer-generated random sequence. Each patient in this study will be aware of his or her own assigned treatment group. At each investigative site, all staff involved in treating and caring for study patients will have full knowledge of treatment assignments for the patients under their care.

In order to maintain the scientific integrity of this trial, access to study data will be strictly controlled prior to the interim and final analyses. For the accumulated group-level data, treatment assignment will not be included, and other parameters that can disclose treatment assignment will be scrambled. Therefore, the sponsor and all investigative sites will remain

blinded to treatment group assignments for the summary statistics and reports until the database lock for the final analysis. Scrambled treatment assignments will be used in the reporting database for Lilly trial-level safety review until the final database lock. Interim analyses will be carried out approximately every 6 months by an independent DMC (external to Lilly) to monitor safety and efficacy. The DMC is unblinded and the Statistical Analysis Center (SAC), which is also external to Lilly, will carry out analyses for the DMC. Until the primary analyses, only the SAC and the DMC will be unblinded to the summary statistics and reports.

For the interim PK analysis to occur prior to the interim/primary analyses, the list of individuals that will have access to unblinded data will be provided with the PK/PD analysis plan, and documentation concerning their access to the data will be retained.

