# 10.2. Health Outcome/Quality of Life Measures

# 10.2.1. Patient-Reported Outcomes

Patient-reported outcomes will be measured using standardized instruments, MDASI-LC and EQ-5D 5L.

Patient-reported questionnaires should be completed by patients when a language translation is available in which the patient is fluent or literate.

At each time point identified in the Schedule of Events (Attachment 1), a paper copy of the questionnaire should be administered to the patient prior to extensive interaction with site staff and study drug administration.

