#### 10.4.3.3. Plasma Samples for Exploratory Biomarker Evaluations

Plasma samples will be collected and analysis may be performed on circulating biomarkers that may play a role in the abemaciclib mechanism of action (refer to Attachment 1). A plasma sample will be collected at baseline prior to randomization. Patients who have entered the study based on a local *KRAS* result may omit this baseline sample; however, it is not a deviation if submitted. This sample will be collected separately at the time of FFPE tumor tissue request. For patients who submitted FFPE tumor tissue in pre-screening, the baseline plasma sample may be drawn at the time of other laboratory blood samples. Additional plasma samples will be collected from all randomized patients on Cycle 1 Day 1 and Cycle 2 Day 1. The evaluation of these samples may involve analysis of DNA, RNA, *KRAS* mutations, and proteins (including any of these components derived from exosomes) to investigate their association with observed clinical outcomes to study drug, and may assist in future development of a liquid biopsy test for *KRAS*. The samples will be coded with the patient number and stored for up to a maximum 15 years unless otherwise determined by government or local law. Details for collecting, processing, and storing the samples are similar to those provided in Section 10.4.3.2.

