## 6.2.3. Definitions and Conventions

Study drug refers to Abemaciclib or erlotinib.

**Study treatment** refers to Abemaciclib + best supportive care or erlotinib + best supportive care.

The **date of randomization** is the date the patient was randomly assigned to Abemaciclib + best supportive care or erlotinib + best supportive care using the interactive web response system (IWRS).

The date of first dose is the date of the first dose of study drug.

The **baseline value of a safety assessment** is the last value observed prior to the first dose of study drug.

The **baseline value of an efficacy assessment** is the last value observed prior to the date of randomization. If a patient's first assessment occurs after randomization but prior to the first dose, this assessment will be used as the baseline.

The study day of a safety event or assessment will be calculated as:

- the difference between the date of the event or assessment and the date of first dose plus 1 for all events or assessments occurring on or after the day of first dose. For example, if an event occurs on 08JUN2014 and the date of first dose was 06JUN2014, the study day of the event is 3.
- the difference between the date of the event or assessment and the date of first dose for all events or assessments occurring before the day of first dose. For example, if an event occurs on 05JUN2014 and the date of first dose was 06JUN2014, the study day of the event is -1.

The study day of an efficacy event or assessment will be calculated as:

- the difference between the date of the event or assessment and the date of randomization plus 1 for all events or assessments occurring on or after the date of randomization.
- the difference between the date of the event or assessment and the date of randomization for all events or assessments occurring before the date of randomization.

One **month** is defined as 365/12 days.

Unless otherwise noted, **summaries of continuous variables** will include a mean, median, standard deviation, minimum, and maximum.

Unless otherwise noted, **summaries of categorical variables** will include the frequency and percentage (relative to the population being analyzed) of each category.

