## 6.2.13. Health Outcomes and Quality of Life Evaluations

Patient-reported outcomes are measured through paper versions of the following:

- MD Anderson Symptom Inventory- Lung Cancer (with 11 exploratory items for brain metastases (9) and potential toxicities (2))
- EuroQol 5-Dimension 5 Level (EQ-5D 5L)

Data from the MDASI-LC instrument will be scored as described by Mendoza and colleagues (Mendoza et al. 2011).

Descriptive statistics will be used to describe several subscales and individual items by treatment arm and cycle: symptom severity (13 core items plus lung-cancer items), core severity (13 core items only), interference (6 interference items), 6 individual brain symptom items: irritability (affective); understanding, speaking, concentrating (cognitive); seizures (focal neurologic); appearance (generalized/ disease status) as well as 3 individual items headache, diarrhea and rash.

For each instrument, the analysis will include all cycles for which instrument is planned to measure and at least 25% of patients in each arm have an assessment. If the above criteria are met, a mixed model will be applied to compare treatment arms for symptom severity, core severity, interference subscales, each of 6 individual brain symptom items (irritability, understanding, speaking, concentrating, seizures, and appearance) as well as 3 individual items: headache, diarrhea and rash. The model will include baseline score as a covariate and an unstructured covariance matrix will be utilized if it converges. If the model cannot converge with an unstructured covariance matrix, the covariance matrix will be determined based on the Akaike Information Criterion (AIC).

If a patient does not complete all items on the MDASI-LC, the mean score for a subscale will be calculated when at least 50% of the items for that subscale were answered).

Based on literature (Farrar et al. 2001), it is suggested that worsening of pain by 2 points may be clinically relevant. Time to worsening in pain (worsening by 2 or more points in MDASI pain item or in WHO ladder code based on Table JPBK.6.5 whichever occurs first) will be described using the method of Kaplan and Meier and will be compared between 2 arms by a log-rank test. Worsening-free pain rate at 3, 6, 9, and 12 months (if available) will be compared between treatment arms.

Code	Description
0	No analgesia
1	Aspirin (for pain, not cardiovascular prophylaxis), acetaminophen, nonsteroidal anti-inflammatory drugs

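### Baseline MDASI-LC and EQ-5D 5L need not precede randomization, and the SAP can accept a post-randomization form as baseline in this open-label trial

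*Protocol*

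**What the plan says.** - **Timing.** Protocol Attachment 1, footnote w: "MDASI-LC and EQ-5D 5L should be administered at baseline (within 14 days of treatment start". The anchor is treatment start. The same footnote asks patients to complete the forms before they interact with site staff.
- **Baseline period.** Protocol 8.1: it "begins when the study ICF is signed and ends at the first study treatment", so it spans randomization.
- **Order.** Protocol 10.2.1: the paper questionnaire "should be administered to the patient prior to extensive interaction with site staff and study drug administration". Randomization is not mentioned.
- **Interval to first dose.** The assignment text between Protocol 9.2 and 9.4 asks for treatment to start promptly but sets no maximum number of days.
- **Knowledge of arm.** Protocol 9.5: "Each patient in this study will be aware of his or her own assigned treatment group".
- **SAP baseline.** SAP 6.2.3: an efficacy baseline "is the last value observed prior to the date of randomization". The fallback is that if a patient's "first assessment occurs after randomization but prior to the first dose, this assessment will be used as the baseline". A safety baseline is the last value before first dose. The SAP assigns the questionnaires to neither definition.
- **Use of baseline.** SAP 6.2.13, on MDASI-LC: "The model will include baseline score as a covariate". The same holds for the EQ-5D index and VAS. Protocol 12.2.11.1 uses baseline as the reference for maximum change in the MDASI-LC composites and worst pain. The 2-point pain-worsening endpoint in SAP 6.2.13 implies a baseline reference without naming it.
- **Contrast.** Protocol 10.4.3.3: "A plasma sample will be collected at baseline prior to randomization".

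**The concern.** Adjusting for a baseline covariate is safe in a randomized comparison because allocation cannot have influenced it. A symptom or health-status score given by a patient who already knows the arm does not carry that guarantee. Patients could plausibly react to the allocation: Protocol 5.5 reports that the FDA narrowed the erlotinib indication in October 2016, and that the NCCN guidelines then dropped erlotinib for patients like these without EGFR mutations. If such baselines enter the models, the between-arm difference in patient-reported scores depends partly on when the form was filled in. These comparisons serve a secondary objective.

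**Working it through.** **Step 1. Is a late form compliant?** Take a patient who is randomized, learns the arm, and completes the first questionnaire on arrival at Cycle 1 Day 1, before meeting staff and before dosing. The form is within 14 days of treatment start, inside the baseline period, and ahead of staff contact and study drug. It breaks no stated timing rule, and the SAP fallback accepts it.

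**Step 2. Who is affected?** The answer depends on which SAP definition applies.

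| Forms completed | Efficacy definition uses | Safety definition uses |
|---|---|---|
| Before randomization only | the early form | the early form |
| Before, and again between randomization and first dose | the early form | the late form |
| Only between randomization and first dose | the late form | the late form |

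The schedule asks for one baseline form, so the middle row should be uncommon. A form completed earlier on the day of randomization is not before that date, so the efficacy wording leaves it unclear.

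**Step 3. How large could it be?** The plan gives no figure to reproduce. The inputs below are assumptions:
- *f*: the share of baselines completed after randomization, 10% to 100%.
- *d*: the shift on learning the arm, 0.25 SD, in one arm and at baseline only.
- *ρ*: the correlation of baseline with follow-up, 0.3 to 0.7.
- True effect zero; 270 and 180 patients, as in the sample-size section.

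Absolute bias is ρ × f × d for ANCOVA and f × d for a change score. At f = 10%, ANCOVA gives 0.3 × 0.10 × 0.25 = 0.0075 to 0.7 × 0.10 × 0.25 = 0.0175 SD. Type I error comes from 2,000 simulated trials per scenario, with a Monte Carlo standard error near 5% of √(0.05 × 0.95 / 2000) ≈ 0.5 percentage points.

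| f | ANCOVA bias (SD) | ANCOVA type I error | Change-score bias (SD) | Change-score type I error |
|---|---|---|---|---|
| 10% | 0.0075–0.0175 | 4.6–5.2% | 0.025 | 5.1–6.0% |
| 25% | 0.019–0.044 | 6.1–10.0% | 0.0625 | 9.6–14.2% |
| 50% | 0.0375–0.0875 | 6.9–23.8% | 0.125 | 19.3–38.2% |
| 100% | 0.075–0.175 | 13.7–71.3% | 0.25 | 59.0–92.0% |

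The simulation uses one follow-up value per patient, so it illustrates the SAP's repeated-measures models and does not reproduce them.

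**Step 4. Does the direction hold if the shift persists?** Patients know their arm throughout. If later answers move by *d* as well, the bias becomes d(1 − ρf) for ANCOVA and d(1 − f) for change. With f = 0.5 and ρ = 0.5:
- Shift at baseline only: −0.5 × 0.5 × 0.25 = −0.0625 SD.
- Persistent shift: 0.25 × (1 − 0.25) = +0.1875 SD.

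The sign reverses. Under persistence the bias is largest at f = 0, where it is +0.25 SD and is simply the open-label reporting effect.

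**The case against.** The strongest reply is that late completion should be the exception. Attachment 1 places both instruments at Visit 0, in the same column (14 days or less) as the eligibility evaluation and ECOG status. Eligibility, and ECOG as a stratification factor, must be known before randomization. Neither form is scheduled on Cycle 1 Day 1. The SAP's first choice is already the pre-randomization value. All this stands: late forms are probably a minority, though no passage limits them.

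The second reply is that open-label reporting after baseline is the larger problem and that the fix does not touch it. Step 4 supports this. The case for the fix is therefore narrower. It keeps the covariate free of allocation, so that the estimated difference does not depend on the mix of early and late forms.

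The third reply is that the plasma sample is a weak contrast, because its collection is linked to the tissue request for KRAS testing. That also stands. It shows only that the protocol can anchor a baseline item to randomization.

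The gap itself is not rebutted. If the questionnaires are not efficacy assessments, their baseline is either undefined or falls under the safety rule, which is no better.

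**Conclusion.** The point holds as a modest, cheaply repaired gap. The protocol permits a post-randomization baseline questionnaire, and SAP 6.2.3 can use it. It affects patients with no pre-randomization form and, under the safety definition, also those who completed a later one. Under the Step 3 assumptions it is negligible at about 10% late completion and material only if late completion is common. The true share, size and direction cannot be found in the documents.

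A reader might infer more, but three stronger readings are not supported:
- **Every patient-reported comparison is compromised.** The WHO-ladder part of the pain endpoint rests on analgesic records, and the EQ-5D item summaries are descriptive. The efficacy rule also protects any patient with a form from before the randomization date.
- **The bias is known to run one way because of the erlotinib label change.** Step 4 shows that the sign depends on whether the shift persists. The FDA restricted the indication, and Protocol Section 5 still describes erlotinib as the approved third-line drug in selected geographies.
- **No later analysis can help.** A missing pre-randomization value cannot be recovered, but leaving out late values shows how sensitive the result is.

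The primary OS analysis is untouched.

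**What to change.** 1. In Attachment 1 footnote w and Protocol 10.2.1, require both questionnaires after the study ICF is signed and before randomization, keeping the 14-day window.
2. In SAP 6.2.3, define the patient-reported baseline as the last questionnaire completed before randomization, counting a form completed earlier on the day of randomization. State that the safety definition does not apply.
3. Flag patients whose only baseline form falls between randomization and first dose. If those values are kept as substitutes in the main models, repeat the MDASI-LC and EQ-5D models without them as a sensitivity analysis, and report the number flagged by arm.

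The cost is a sentence in each of the two protocol places, a SAP definition and one extra model run. No visit is added, because eligibility work already precedes randomization. The order of same-day forms must be recorded. The protocol change helps only patients not yet randomized, but the SAP changes can be made at any time before database lock. The downside is that a few patients will have a flagged or missing baseline. SAP 6.2.4 imputes nothing except dates, so those left out of the sensitivity run drop from the baseline-adjusted models.
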